6.1. Outcome Measures

The primary study endpoint will be remission rates based on the 16-item Quick Inventory of Depressive Symptomatology, Self-Report (QIDS-SR), which will be extracted from the 30-item Inventory of Depressive Symptomatology (IDS-SR). QIDS-SR measures MDD severity; a score of 5 or less is considered remission. The secondary study endpoints will be: a) improvement in social and occupational function according to the 5-item self-administered Work and Social Adjustment Scale and b) side effect measures using the 3-item Frequency, Intensity, and Burden of Side Effects Rating (FIBSER) scale.

6.2. Demographics Forms

Demographics Form: The demographics form will be administered to all participants during the screening phase. The form consists of basic demographic information (e.g., gender, race/ethnicity, education).

6.3. Clinical, General Health, and Medical History Surveys

Self-Administered Comorbidity Questionnaire (SCQ): The SCQ assesses the presence of medical problems, whether treatment is received for the condition, and whether or not the condition limits functioning. Each question is answered on a yes/no basis. Each affirmative response to the three items per medical condition is coded as a 1, with the total score being the sum of all positive responses. The medical conditions specified on the SCQ include: heart disease, high blood pressure, lung disease, diabetes, ulcer or stomach disease, kidney disease, liver disease, anemia or other blood disease, cancer, depression, arthritis, thyroid disease and back pain.

Prior and Concomitant Medications: The Prior and Concomitant Medications form assesses prescribed and certain over-the-counter medications taken by the participant. The Prior and Concomitant Medications form will be administered at the baseline visit and at each visit thereafter, if the participant endorses a change in medication status.

Antidepressant Treatment Response Questionnaire (ATRQ): clinician-rated scale used to determine treatment resistance in MDD. The MGH ATRQ defines 6 weeks on an adequate dose of antidepressant medication as an adequate duration of treatment. It also provides specific operational criteria for adequate dosage for each of the most commonly used antidepressants.⁵²

Fagerstrom Test of Nicotine Dependence: The Fagerstrom Test of Nicotine Dependence consists of six items that test for dependence to nicotine. Sample items include "How soon after you awake do you smoke your first cigarette?" with answers including "within 5 minutes", "6-30 minutes", "31-60 minutes" and "after 60 minutes". A scoring algorithm has been created for all items in order to denote ranges of severity of dependence, including "very low dependence," "low", "moderate", "high", and "very high" levels.⁵³

6.4. Depression Severity Measurement Tools

Mini-International Neuropsychiatric Interview: The MINI, Version 7.0. is a structured diagnostic interview designed to screen for Axis I psychiatric disorders in the Diagnostic and Statistical Manual of Mental Disorders (DSM-5). Clinicians complete this structured interview to assess for the presence of various forms of psychopathology, including mood and anxiety disorders; psychotic disorders; anxiety disorders; substance use disorders; eating disorders; and antisocial personality disorders. Our study also adds in specific questions to gauge various specifiers of a major depressive episode, including with anxious distress, atypical or melancholic features. Permission to use this measure has been granted by the measure's lead author, David Sheehan.⁵⁴

Hamilton Depression Rating Scale: a 17-item clinician-administered scale that has been widely used to determine cut-offs for clinical trials and also to determine changes overtime. The items are anchored from 0 to 4 or from 0 to 2 where higher scores indicate worse severity. There are well established cut-offs for this scale: 0-7 = normal; 8-13 = mild depression; 14-18 = moderate depression; 19-22 = severe depression and ≥ 23 very severe depression. The current trial will use moderate depression (i.e., total score of at least 14) as severity cut-off for eligibility.⁵⁵

Inventory of Depressive Symptomatology: Self Report (IDS-SR): a 30-item rating scale designed to assess the severity of depressive symptoms over the past week. The questionnaire assesses the core symptoms of depression such as depressed mood and anhedonia, alongside additional items that measure, for example, anxiety, irritability, insomnia/hypersomnia, somatic complaints and other physical symptoms, panic, and reactivity to interpersonal rejection.⁵⁶

Concise Health Risk Tracking - Self Report: The CHRT-SR is a 16-item participant self-report assessment of suicidality and related thoughts and behaviors. The scale is designed to quickly and easily track suicidality in a manner consistent with the Columbia Classification Algorithm of Suicide Assessment (C-CASA). Items are rated on a fully anchored 5-point Likert scale with responses ranging from 1 (strongly disagree) to 5 (strongly agree), with total scores ranging from 13 to 65. The first 13 items detail suicide propensity and include items measuring passive suicidal ideation and lack of social support. The final 3 items include suicide risk items and measure active suicidal ideation and planning. The CHRT-SR has good internal consistency (Cronbach's alpha of 0.78).⁵⁷

Work and Social Adjustment Scale: consists of 5 items, each on a 0 ("No impairment at all") to 8 ("very severe impairment") scale, that inquires about the impact of one's current feelings on one's employment and psychosocial functioning. Sample items include "Because of the way I feel, my ability to work is impaired" and "because of the way I feel, my ability to form and maintain close relationships with others, including those I live with, is impaired". Internal reliability was at appropriate levels, ranging from Cronbach's alpha = .70 and .94.⁵⁸

The Temporal Experience of Pleasure Scale: this instrument is a self-reported 18-item scale that investigates the two main components anhedonia: 1) anticipatory anhedonia, and 2) consummatory anhedonia. Anticipatory anhedonia (assessed by 10 items) is related to low motivation and impaired goal-directed behavior. Consummatory anhedonia (evaluated by 8 items) is associated with lack of pleasure or inability to satiate a desire. The two components of anhedonia are specific and distinct constructs (Gard et al., 2006). Each item follows a 6-point Likert format where 1 = *very false for me* and 6 = *very true for me*.⁵⁹

Behavioral Inhibition System/Behavioral Approach System Scale: this scale consists of 24 self-reported items that assesses two motivational systems: 1) avoidance/inhibition where the objective is to avoid a situation or stimuli, and 2) drive/appetite to move towards a goal, and (Carver and White, 2013). Each item follows a 4-point Likert format. Each construct (inhibition and activation) had subscales that further explore their components.⁶⁰

6.5. Anxiety Symptoms

The Generalized Anxiety Disorder 7-item Scale (GAD-7): assesses common symptoms of anxiety and serves as an anxiety-severity scale. Participants respond on a 0 to 3 scale, from “not at all” to “nearly every day”, the number of days over the past two weeks that they have been affected by problems including “worrying too much about different things” and “trouble relaxing”. The total score of this scale ranges from 0-21, with scores from 5-9 indicating mild anxiety, scores from 10-14 indicating moderate anxiety, and scores 15 or higher indicating severe anxiety.⁶¹

State-Trait Anxiety Inventory: The 40-item State-Trait Anxiety Inventory includes 20 items indicative of state – or current levels of anxiety – and 20 items of trait – or enduring – anxiety. Items are scored on a four-point scale, ranging from “almost never” to “almost always”, with higher scores indicating higher levels of anxiety. Sample state anxiety items are “I am worried” and “I feel calm” while sample trait anxiety items include “I worry too much over something that doesn’t really matter.” The psychometrics of this measure have been well-established.⁶²

6.6. Side Effects and Adherence

The Patient Adherence Questionnaire (PAQ): two-item inventory that assesses for adherence to antidepressant medication. The first item asks how often participants have taken their medication, with responses ranging from “I have taken my medications every day without missing a day” to “I have stopped taking my medications.” The second item asks about adjustments made to medication, and answer choices include various options about why individuals might have reduced or increased their dosage, or whether medication has always been taken as prescribed. The measure is scored by adding up items that encode if individuals have missed taking their medication two or more days or have reduced or increased their dosage, with any positive response classifying the patient as being “non-adherent” to medication.⁶³

The Frequency, Intensity, and Burden of Side Effects Ratings (FIBSER): used to rate side effects from antidepressant medication. The measure consists of three items, each scored on a 0 to 6 scale, that inquire about the frequency of side effects over the past week (from “no side effects” to “present all the time”); the intensity of such side effects (from “no side effects” to “intolerable”), and the interference on day-to-day functioning due to medication side effects (from “no impairment” to “unable to function”).⁶⁴

6.7. Neurocognitive and Behavioral Phenotyping Tasks

Flanker Test: series of response inhibition tests used to assess the ability of suppress responses that are inappropriate in a particular context. The target is flanked by non-target stimuli which correspond either to the same directional response as the target (congruent flankers), to the opposite response (incongruent flankers), or to neither (neutral flankers).

Digit Symbol Substitution Test: timed standardized neuropsychological test that assess processing speed.

7. Patient Recruitment and Consenting Process

7.1. IRB Review

Before study initiation, the Investigator must have written and dated approval/favorable opinion from the IRB for the protocol, consent form, patient recruitment materials/process (e.g., advertisements), and any other written information to be provided to patients.

7.2. Recruitment

Individuals are going to be recruited from the well-established network developed by the Center for Depression Research and Clinical Care (CDRC) and which includes the Mood Disorders Network, and current CDRC studies such as the Dallas 2K Study (D2K) and the Resilience in Adolescent Development (RAD). The Mood Disorders Network (MDN) consists of primary care practices, psychiatric care practices, charity clinics, community, schools, who are interested in collaborating with CDRC on activities and projects geared toward improving care for those suffering from depression. Many MDN clinical sites use the Vital Sign 6 (VS6) software, an application that allows screening and management of depression, using the principles of Measurement-Based Care (MBC). Using VS6 application, participants are systematically assessed for depression and treatment outcomes are monitored utilizing multi-step evidence-based treatment algorithms.

The D2K is an observational long-term study conducted by the CDRC researching the biological mechanisms of depression and antidepressant treatment response. The D2K study is comprised of 2,000 participants, over 10 years of age, with a lifetime or current diagnosis of a mood disorder. A significant part of the individuals in this study are not taking antidepressants. RAD is a 10-year study of 1,500 participants (ages 10-24) that will help uncover the factors that contribute to resilience among children, adolescents, and young adults at risk for mood and anxiety disorders. In addition to these observational studies, the CDRC conducts clinical trials for which there are standard recruitment processes. Previous participants in research at the CDRC who have provided consent for future contact will be invited to participate in this study. Participants recruited from the CDRC will already be registered under a research protocol and not a part of the principal investigator's clinical practice.

Participants will also be recruited from registries such as the UT Southwestern Research Volunteer Registry, UTSW Family Medicine Clinic, the UTSW General Internal Medicine Clinic and the UTSW Employee Assistance Program. The PI and study psychiatrist will meet with MDs and clinic managers at these sites to explain the study goals, inclusion and exclusion criteria, and study process prior to recruitment. We will provide the MDs with written information about the study and the characteristics desired in referrals. Finally, PRECISE-D will recruit from self- and clinician-referral, and IRB-approved study advertisements.

7.3. Informed Consent

All subjects will receive the consent form for the study as well as the Human Subject's Bill of Rights. First, patients interested in the study will be given a copy of the informed consent form so they can carefully read the document and discuss the research with their family, friends and/or physician and develop questions to ask at their next meeting with the research staff. If they continue to be interested, they will visit the clinic and the investigator will meet with the potential subject to review and to discuss the details of the research study using the informed consent document as a guide. This discussion should include all

of the required elements of informed consent, e.g., the purpose of the research, the procedures to be followed, the risks and discomforts as well as potential benefits associated with participation, and alternative procedures or treatments, if any, to the study procedures or treatments. Subjects will always be given the opportunity to ask questions and have them answered by the investigator and, whenever possible, to consult with friends/family and/or their physicians. Once they have read the consent document and their questions are answered, if they agree to participate in the research, they sign and date the informed consent document. Patients will sign informed consent and only then will any study-related procedures be conducted. In order to remove any undue pressure on patients referred to the study from a study investigator who happens to be their personal clinician, such interested patients will first have an opportunity to inquire about the study from a research assistant, and obtain a copy of the consent form in advance. In addition, when presenting for screening, they can only be screened and followed during the study (if eligible) from an investigator who is different than their personal clinician.

8. Potential Risks

Human subject risk related to administration of antidepressant medication is minimal as the medications planned for use in this study, escitalopram and bupropion, are approved by the Food and Drug administration and are frequently prescribed in routine practice and for time-periods that are consistent with recommended treatment practices. Additionally, the routine assessment of side effects with measures such as the FIBSER will enable quick detection of adverse effects if they are present.

The risks involved in drawing blood from a vein may include, but are not limited to, momentary discomfort at the site of the blood draw, possible bruising, redness, and swelling around the site, bleeding at the site, feeling of lightheadedness when the blood is drawn, and rarely, an infection at the site of the blood draw.

The risks of finger stick for the point of care (POC) C-reactive protein (CRP) testing include excessive bleeding, bruising/discoloration, infection, dizziness, fainting and pain. These risks are comparable to routine clinical practice where venous blood work and finger stick tests are routinely used for management of chronic medical conditions.

The risk of EEG includes discomfort from wearing a close-fitting elastic cap and the use of an electrolyte solution (KCl, similar to salt water).

The risk of loss of privacy is judged to be low. However, patients will be asked to provide personal identifying information, and there is a very rare risk of breach of confidentiality.

9. Subject Safety and Data Monitoring

9.1. Safety Measures

Minimal risk is expected from the medications as FDA approved low doses will be administered initially, side-effects to these doses monitored and dosage adjustments made according to guidelines. If physical adverse effects are intolerable at the lowest therapeutic dose, subjects may leave the study and will be offered an alternative treatment in consultation with their provider. Minimal risk is also expected from venipuncture and finger stick for POC CRP testing. These will be further minimized by having laboratory work performed only by trained and certified staff, following aseptic procedures, and ascertaining that patient does not have an active infection or taking immunosuppressive treatment (as part of eligibility criteria).

All research personnel are trained in safety precautions in the event the patient needs immediate clinical management or an imminent clinical issue is identified.

9.2. Suicide Monitoring

Participants who report risk of self-harm at any point of contact will be thoroughly evaluated by the study personnel for intent, plan and means for suicide. If the participant is in the clinic, the study clinician will be immediately notified to further assess the participant. If the participant is deemed an acute risk for suicide, the physician will direct the measures necessary to get the participant to safety, using clinic specific crisis management procedures. If study personnel learn that a participant may be at acute risk during a phone assessment, a complete evaluation of the situation will become necessary. For example, if the participant indicates thoughts of suicide/death several times a day on the CHRT scale, the study team will obtain information about the participant's intent, plan, and means at hand for suicide, as well as determine the location of the participant and whether anyone else is with the participant. Measures to keep the participant safe, including the option of calling 911 for police assistance will be implemented.

Specifically:

- In the event that a participant contacts the study and indicates suicidal ideation with intent
- Study personnel will determine if participant is alone or has supportive family or friends with him.
- Personnel will contact family members/significant friends using the contact information provided by participant at study entry.
- If family is contacted, they will be alerted to the urgency and need to limit the participant's access to the means of suicide. Personnel will review plan with family should participant need urgent care to prevent a suicide attempt.

Whether the participant presents in clinic or calls in expressing active suicidality, the clinician or study personnel will instruct the participant to go to the nearest emergency room. If family or friends are not available to take the participant to the emergency room, or if the participant refuses, the clinician/study personnel may call 911 and have the participant escorted involuntarily. In situations where participants have made initial contact with the study personnel and not the study clinician, the study personnel will notify the licensed treating clinician of the event. Following resolution of the acute suicidal status, the participant will be evaluated for continuation in the study. This will be based on the current need for best clinical care.

9.3. Reasons for Early Termination

Acceptable reasons for early termination from the randomized clinical trial include the following: 1) request of patient, 2) decision of physician, 3) serious adverse event and 4) protocol violation. Patients will be assessed for suicidal ideation at every visit. Subjects who, in the opinion of the assessing clinician have a worsening of suicidal ideation that renders them at increased risk for study participation will be removed from the study and given an appropriate clinical referral.

9.4. Evaluation of Adverse Events (AEs)

An adverse event is any untoward medical occurrence in a study subject. The reporting period begins when a study subject signs consent and ends at Week 12 or earlier for patients who prematurely discontinue the study.

Adverse events will be recorded using the appropriate form. Patients shall be allowed to contact the investigator or a member of his staff at any time between visits concerning adverse events or worsening of symptoms.

Unanticipated problems involving risks to subjects, including adverse events, will be reported to the overall study PI and to the site IRB.

Serious adverse events, including those spontaneously reported to the site-investigator from the time a signed and dated ICF is obtained until within 30 days after the last dose of study drug must be reported using the Serious Adverse Event Form.

Pregnancy

If a subject (or subject's partner) becomes pregnant during the study, it must be reported within 24 business hours of the time the investigator becomes aware of the event to study PI and site IRB. Pregnancy in itself is not regarded as an AE unless there is a clinical suspicion that a study drug may have interfered with the effectiveness of a contraceptive medication. Any pregnancy that occurs from the first day of treatment to 30 days following the last treatment given will be followed for gestational outcome.

Disease Progression or Worsening Depression

The development of worsening depression should be considered as disease progression and not an AE. Events, which are unequivocally due to disease progression, should not be reported as an AE during the study.

Serious Adverse Events (SAEs)

The following criteria define an SAE: a) death, b) life-threatening event, c) hospitalization or prolongation of hospitalization, d) persistent or significant disability/incapacity, or e) congenital anomaly/birth defect. The study PI are in charge of determining if an adverse event represents an SAE.

10. Procedures to Maintain Confidentiality

All investigators are required to prepare and maintain adequate and accurate case histories designed to record all observations and other data pertinent to the investigation on each individual treated in the investigation.

All research staff will receive training through the Collaborative Institutional Training Initiative. Required courses will include: HIPAA, Good Clinical Practice, and Human Subject Protection. Staff will only have access to identifying information as needed for their role in the study. No information about or provided by the subjects will be disclosed to others without written permission. Electronic health records will be stored on password-protected, secure networks or devices.

Potential risks to data confidentiality will be mitigated by requirements for the de-identification of all data and by security protocols for all data capture systems. As with all research data, information gathered by the study will be used only for aggregate analysis. It will not be released with any information that identifies research participants. Uses and risks related to data collection will be outlined in the informed consent and reviewed with the subjects.

11. Potential Benefits to Study Participants and Others

Study participants will have the opportunity to directly benefit from the antidepressant medications escitalopram and bupropion. It is expected that a subset of patients in both treatment arms will show either improvement in or remission of their disorder. The population of depressed patients as a whole has an opportunity to benefit from the study, as the results may be valuable in prescribing appropriate personalized treatment strategies in the long-term treatment of depression.

If we find that CRP-consistent antidepressant selection is superior to CRP-inconsistent antidepressant selection, it will reduce the decisional uncertainty associated with antidepressant selection in routine clinical practice and allow treatment providers and patients to choose an antidepressant that is more likely to result in favorable treatment outcomes. If favorable, this study would also support personalized selection of antidepressant medications to individual MDD patients using a readily-available inexpensive blood test. Additionally, if the secondary analysis demonstrates that finger stick blood can be used for the CRP test instead of venous blood, then this will represent a direct point-of-care option.

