3.1. Overview

The current study is single site, randomized, open label 8-week clinical trial comparing the efficacy of CRP-consistent antidepressant selection vs CRP-inconsistent antidepressant selection. Venous levels of CRP will be measured by an FDA cleared Point of Care Smart analyzer (Diazyme Laboratories) and/or Quest Diagnostics, which provides the CRP concentration within few minutes. The study will use a stratified randomization (i.e. separate randomization schemes for patients with POC CRP ≥ 1 and POC CRP < 1). This will assure that the four study groups have similar sample sizes: 1) escitalopram with CRP < 1 , 2) bupropion-XL with CRP < 1 , 3) escitalopram with CRP ≥ 1 , 4) bupropion-XL with CRP ≥ 1 . We anticipate that participants with higher inflammation (CRP ≥ 1) will have higher remission rates with bupropion-XL than escitalopram, while individuals with low levels of systemic inflammation (CRP < 1) will remit more frequently with escitalopram when compared to those treated with bupropion XL. A sub-study will compare POC CRP levels based on the blood source: venous blood obtained by venipuncture vs capillary blood obtained via fingerstick.

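### Protocol section 9.4 lists hospitalisation as an SAE criterion but rules worsening depression not to be an AE, so a psychiatric admission can go unreported as an SAE

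*Protocol*

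**What the plan says.** Four statements in Protocol section 9.4 bear on this point:

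- The general definition: "An adverse event is any untoward medical occurrence in a study subject".
- The progression rule, in two sentences: "The development of worsening depression should be considered as disease progression and not an AE" and "Events, which are unequivocally due to disease progression, should not be reported as an AE during the study".
- The SAE list. Its items include death, life-threatening events and "c) hospitalization or prolongation of hospitalization". No item is qualified by cause.
- The route to SAE status: "The study PI are in charge of determining if an adverse event represents an SAE".

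Two other places matter. Section 9.3 provides that participants who, in the assessing clinician's opinion, "have a worsening of suicidal ideation that renders them at increased risk for study participation will be removed from the study". Section 3.1 describes the design: "The current study is single site, randomized, open label 8-week clinical trial".

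**The concern.** In a trial of major depression, the serious psychiatric events to be expected are admissions and suicidal crises arising from the depression itself. The protocol foresees them: section 9.2 sets out how acutely suicidal participants are sent to an emergency room, but mentions no AE or SAE form. Section 9.4 then gives two incompatible instructions for the same event. Two investigators who both follow it carefully could handle one psychiatric admission in opposite ways.

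What is at stake is the completeness of SAE reporting and the safety comparison between the arms. What counts as an AE or SAE is fixed at the point of recording, in the protocol. A later analysis plan cannot tabulate events that were never recorded.

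**Working it through.** The plan gives no figure on this point to reproduce, and no rate of worsening or hospitalisation. The check is mainly textual.

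**Step 1. Apply section 9.4 to one case: a participant is admitted because the depression has become severe.**

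| Rule in 9.4 | Result for this admission |
|---|---|
| General AE definition | It is an AE |
| Progression rule, first sentence | Worsening depression is not an AE; no exception for seriousness |
| Progression rule, second sentence | Not reported as an AE if unequivocally due to progression; no exception for seriousness |
| SAE list | Meets the hospitalisation criterion |
| Route to SAE status | Decided for an adverse event, so an event already ruled out as an AE need not reach this decision |

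The general definition and the SAE list point to reporting. The progression rule points away from it, and the route to SAE status lets that exclusion carry through. No sentence ranks them. A life-threatening event attributed to the depression runs through the same table with the same result.

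**Step 2. How far the word *unequivocally* limits the rule.** It stands in the second sentence only, so events of doubtful cause remain reportable under that sentence. The first sentence excludes worsening depression without the qualifier. An admission for severe depression is also the case most easily called unequivocal.

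**Step 3. Could a loss differ by arm?** Allocation is 1:1 within each CRP stratum (section 3.2), so 70 / 2 = about 35 participants per arm. Treatment is open label, and no blinded attribution of events to progression is described. Section 3.1 expects fewer remissions on the CRP-inconsistent drug in both strata. Unequal loss is therefore possible. The protocol does not establish that it is likely.

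**Step 4. Scale.** One unreported event changes an arm's SAE proportion by 1 / 35 = 2.9 percentage points. As an assumption only, if 2% to 10% of participants had a serious deterioration, 0.02 × 70 = 1.4 to 0.10 × 70 = 7 events in the whole trial would come under the conflicting rules. That is the number exposed to the ambiguity, not the number lost.

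**Step 5. Does Aim 3 depend on these records?** Aim 3 (section 2.2) compares the arms on adverse effects of antidepressant treatment. The matching endpoint in section 6.1 is FIBSER, a three-item scale that section 6.6 describes as rating medication side effects. AE forms, SAE forms and admissions do not enter it.

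**The case against.** The strongest reply is that the SAE duty stands on its own. Section 9.4 requires SAEs to be reported on the SAE form up to 30 days after the last dose, lists hospitalisation without qualification, and nowhere says that an SAE due to depression is exempt. The progression rule speaks only of reporting as an AE. This reading is possible and may be what was intended. No sentence states it, however, and the wording that decides SAE status for an adverse event points the other way.

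A second reply is that worsening is captured elsewhere. The IDS, CHRT and WSAS are scheduled at baseline and Weeks 2, 4, 6, 8 and 12, the Hamilton scale is repeated at Weeks 8 and 12, and suicidal ideation is assessed at every visit. This justifies keeping ordinary symptom change out of the AE counts, since worsening is the efficacy construct here. It does not answer the point about serious events, because none of these scales records an admission or a life-threatening event as an SAE.

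A third reply is that unanticipated problems go to the study PI and the site IRB, by a route wider than AEs. That route remains, so a reader should not infer that oversight would be blind to these events. But section 9.4 itself anticipates worsening depression, so the route is not a dependable substitute for SAE reporting.

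A reader might also infer that the protocol predicts more deterioration in the CRP-inconsistent arm. It predicts different remission rates and nothing about worsening or admissions, and both arms receive an approved antidepressant. Fewer remissions need not mean more deterioration.

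**Conclusion.** The contradiction within section 9.4 is real and should be resolved. As written, the text permits a psychiatric hospitalisation or life-threatening event attributed to depression to go unreported as an SAE, and in an open-label trial any such loss could be uneven between the arms. It does not show that this will happen. The size cannot be given: there are no event rates, and the counts above rest on an assumed range.

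Two stronger conclusions should not be drawn. The rule does not bias Aim 3, because FIBSER never counted AEs, SAEs or admissions. Nor does it follow that serious deteriorations would vanish from the safety table in both arms. That would require every event to be judged progression and the SAE duty to be set aside each time.

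**What to change.** Reconcile the statements in section 9.4:

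1. State that any event meeting an SAE criterion is recorded and reported as an SAE even when it is attributed to worsening depression.
2. Limit the progression exclusion to non-serious symptom change that the rating scales already capture.
3. In the safety summary, and not under Aim 3, tabulate by arm these SAEs and the study removals for worsening suicidal ideation.

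This changes reporting only; the rules on removal and on handling acute suicidality are untouched. The cost is one or two sentences in the protocol, a few more SAE forms and a slightly less favourable safety table.
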